20. APPENDIX B: CALCULATION OF MODIFIED RODNAN SKIN SCORE

The mRSS is displayed below.

[figure not shown]
21. APPENDIX C: SCLERODERMA HEALTH ASSESSMENT QUESTIONNAIRE

The SHAQ-DI is displayed below:

SHAQ - USA/English (original) 8HAQ_AU2.0_eng-USori

Source: https://eprovide.mapi-trust.org/instruments/scleroderma-health-assessment-questionnaire

22. APPENDIX D: PHYSICIAN GLOBAL ASSESSMENT

23. APPENDIX E: PATIENT GLOBAL ASSESSMENT

24. APPENDIX F: DETERMINING RELATIONSHIP OF ADVERSE EVENTS TO STUDY DRUG

Determination the relationship of AEs to study drug is displayed below. (27)

1 NOT RELATED

This category applies to those AEs, which, after careful medical consideration, are clearly felt to be due to extraneous causes (e.g., disease, environment, etc.) that are unrelated to the administration of study drug.

2 UNLIKELY RELATED (must have first 2)

This category applies to those AEs, which, after careful medical consideration, are felt unlikely to be related to the administration of the study drug. The relationship of an AE to the study drug can be considered unlikely if:

- It does not follow a reasonable temporal sequence from administration of the drug.
- It could readily have been a result of the subject's clinical state, environmental or toxic factors, or other modes of therapy administered to the subject.
- It does not follow a known response pattern to the suspected drug.
- It does not reappear or worsen when the drug is re-administered.

POSSIBLY RELATED (must have first 2)

[figure not shown]
This category applies to those AEs, which, after careful medical consideration, are felt unlikely to be related to the administration of the study drug, but the possibility cannot be ruled out with certainty. The relationship of an AE to the study drug can be considered possible if:

- It follows a reasonable temporal sequence from administration of the drug.
- It could readily have been a result of the subject's clinical state, environmental or toxic factors, or other modes of therapy administered to the subject.
- It follows a known response pattern to the suspected drug.

4 **PROBABLY RELATED** (must have first 3)

This category applies to those AEs, which, after careful medical consideration, are felt with a high degree of certainty to be related to the administration of the study drug. The relationship of an AE to the study drug can be considered probable if:

- It follows a reasonable temporal sequence from administration of the drug.
- It could not be reasonably explained by the known characteristics of the subject's clinical state, environmental or toxic factors or other modes of therapy administered to the subject.
- It disappears or decreases upon cessation of drug or reduction in dose.*
- It follows a known response pattern to the suspected drug.

5 **DEFINITELY RELATED** (must have first 3)

This category applies to those AEs, which, after careful medical consideration, are felt to be related to the administration of the study drug. The relationship of an AE to the study drug can be considered related if:

- It follows a reasonable temporal sequence from administration of the drug or drug levels have been established in body fluids or tissues.
- It could not be reasonably explained by the known characteristics of the subject's clinical state, environmental or toxic factors or other modes of therapy administered to the subject.
- It disappears or decreases upon cessation of drug or reduction on dose and appears upon rechallenge.*
- It follows a known response pattern to the suspected drug.

Adapted from Cobert, B (2012). Cobert's Manual of Drug Safety and Pharmacovigilance (2nd Ed). Massachusetts: Jones & Bartlett Learning, LLC.

^{*}There are exceptions when an AE does not disappear upon discontinuation of the drug, yet drug relatedness clearly exists.

25. APPENDIX G: DRUGS THAT INDUCE AND INHIBIT CYP3A4

This is not a comprehensive list, and all concomitant medications should be evaluated for possible interactions with belumosudil. (28)

Examples of Clinical Inducers / Inhibitors of CYP3A4

	Strong	Moderate	Weak
Inducers	Carbamazepine	Bosentan	Armodafinil
	Enzalutamide	Efavirenz	Rufinamide
	Mitotane	Etravirine	
	Phenytoin	Modafinil	
	Rifampin		
	St. John's wort		
Inhibitors	Boceprevir	Aprepitant	Chlorzoxazone
	Cobicistat	Cimetidine	Cilostazol
	Conivaptan	Ciprofloxacin	Fosaprepitant
	Danoprevir	Clotrimazole	Istradefylline
	Dasabuvir	Crizotinib	Ivacaftor
	Elvitegravir	Cyclosporine	Lomitapide
	Grapefruit juice	Dronedarone	Ranitidine
	Indinavir	Erythromycin	Ranolazine
	Itraconazole	Fluconazole	Tacrolimus
	Ketoconazole	Fluvoxamine	Ticagrelor
	Lopinavir	Imatinib	
	Paritaprevir	Tofisopam	
	Ombitasvir	Verapamil	
	Posaconazole		
	Ritonavir		
	Saquinavir		
	Telaprevir		
	Tipranavir		
	Troleandomycin		
	Voriconazole		

Source:

 $\frac{https://www.fda.gov/drugs/developmentapprovalprocess/developmentresources/druginteractionslabeling/ucm093664.htm\ Accessed\ 05\ Apr\ 2018$

26. APPENDIX H: DRUGS KNOWN TO HAVE THE POTENTIAL FOR QTC PROLONGATION

Drugs known to have the potential for prolonging of QTc are prohibited. The list below is not comprehensive. All concomitant medications should be evaluated for possible interactions with belumosudil. (29)

Drugs Known to Prolong QTc

	Generic Name
• Aclarubicin	Iloperidone
• Amiodarone	Levofloxacin
• Anagrelide	• Levomepromazine
Arsenic trioxide	Levomethadyl acetate
• Astemizole	 Levosulpiride
Azithromycin	Mesoridazine
• Bepridil	• Methadone
• Chloroquine	Moxifloxacin
• Chlorpromazine	• Ondansetron
• Cilostazol	Oxaliplatin
 Ciprofloxacin 	Papaverine HCl
Cisapride	Pentamidine
Citalopram	Pimozide
Clarithromycin	• Probucol
• Disopyramide	 Procainamide
• Dofetilide	 Propofol
• Domperidone	Quinidine
• Donepezil	Roxithromycin
• Dronedarone	 Sevoflurane
 Droperidol 	• Sotalol
• Erythromycin	 Sparfloxacin
• Escitalopram	Sulpiride
• Flecainide	Sultopride
• Fluconazole	Terfenadine
Gatifloxacin	Terlipressin
Grepafloxacin	Terodiline
Halofantrine	Thioridazine
Haloperidol	• Vandetanib
• Ibogaine	
• Ibutilide	

Source: https://crediblemeds.org/pdftemp/pdf/CombinedList.pdf Accessed 04 Jun 2018

ALP	Alkaline phosphatase
ALT	Alanine aminotransferase
AST	Aspartate aminotransferase
ATC	Anatomical Therapeutic Class
BID	Twice daily
BMI	Body mass index
CI	Confidence interval
CM	Concomitant medication
CRF	Case report form
CRISS	Combined Response Index in Diffuse Cutaneous Systemic Sclerosis
CTCAE	Common Terminology Criteria for Adverse Events
dcSSc	Diffuse cutaneous systemic sclerosis
DL _{co}	Diffusing capacity of the lungs for carbon monoxide
ECG	Electrocardiogram
EOT	End of Treatment
FEV ₁	Forced expiratory volume (in the first second)
FVC	Forced vital capacity
GFR	Glomerular filtration rate
GGT	Gamma-glutamyl transferase
Hb	Hemoglobin
HLGT	High level group term
HRCT	High-resolution computerized tomography
IEC	Independent Ethics Committee
ILD	Interstitial lung disease
IND	Investigational New Drug
IRB	Institutional review board
ICH	International Conference on Harmonisation
LOCF	Last observation carried forward
MedDRA	Medical Dictionary for Regulatory Activities
mITT	Modified intent-to-treatment
MMRM	Mixed-effects Model of Repeated Measures
[name]

F	
mRSS	Modified Rodnan Skin Thickness Score
PA	Primary analysis
PD	Pharmacodynamic
PDI	Planned dose intensity
PE	Physical exam
PFTs	Pulmonary function tests
PK	Pharmacokinetic
PT	Preferred term
QD	Once daily
QTcF	Corrected QT interval using Fridericia's formula
RDI	Relative dose intensity
RV	Residual volume
SAE	Serious adverse event
SAP	Statistical analysis plan
SD	Standard deviation
SHAQ-DI	Scleroderma Health Assessment Questionnaire-Disability Index
SOC	System organ class
SSc	Systemic sclerosis
TEAE	Treatment emergent adverse event
TLC	Total lung capacity
VAS	Visual Analog Scale
WHO	World Health Organization

1 INTRODUCTION

This Statistical Analysis Plan (SAP) describes data-handling and statistical procedures to be used for Study KD025--209 as specified in protocol (Amendment No. 4, 27 May 2021): A Phase 2, Randomized, Placebo-controlled, Double-blind, Open-label Extension Multicenter Study to Evaluate the Efficacy and Safety of Belumosudil (KD025) in Subjects with Diffuse Cutaneous Systemic Sclerosis.

Pharmacokinetic (PK), Pharmacodynamic (PD) and exploratory objectives analyses (biomarkers analysis, histology and gene expression analyses) will be described in separate documents.

The SAP was written in accordance with the recommendations outlined in the International Conference on Harmonisation (ICH) E9 Guideline entitled "Guidance for Industry: Statistical Principles for Clinical Trials" and the most recent ICH-E3 Guideline, entitled "Guidance for Industry: Structure and Content of Clinical Study Reports."

2 STUDY SUMMARY

2.1 Study Objectives

2.1.1 Primary objective

 To evaluate the efficacy of belumosudil compared to placebo for the Combined Response Index in diffuse cutaneous Systemic Sclerosis (CRISS) at Week 24 in modified Intent-to-Treatment (mITT) population.

2.1.2 Secondary objectives

- To assess the CRISS for each group at Week 52
- To evaluate the efficacy of belumosudil compared to placebo at Week 24 for:
 - Modified Rodnan skin thickness score (mRSS)
 - Forced vital capacity (FVC)
 - Physician global assessment
 - Patient global assessment
 - Scleroderma Health Assessment Questionnaire-Disability Index (SHAQ-DI)
- To evaluate the efficacy of belumosudil at Week 52 compared to baseline for subjects randomized to belumosudil for the parameters in the bullet above
- To assess changes in lung fibrosis, via high resolution computerized tomography (HRCT), performed at baseline, Weeks 24 and Week 52 only in subjects with ILD at screening.

 To assess the safety of belumosudil compared to placebo in subjects with diffuse cutaneous systemic sclerosis (dcSSc) by examining the percentage of subjects with Treatment-emergent AEs (TEAEs) (Common Terminology Criteria for Adverse Events [CTCAE] v5.0) in subjects with dcSSc

2.2 Study Design

KD025-209 is a Phase 2, placebo-controlled, double-blinded, randomized, multicenter trial in subjects with dcSSc with an open-label extension. The study schematic is shown below in Figure 1.

Subjects who have signed an Institutional Review Board (IRB)/ Independent Ethics Committee (IEC)-approved informed consent form and met all of the inclusion and do not meet all of the exclusion criteria will be enrolled. A total of 60 subjects will be randomized into 3 groups (1:1:1) to receive orally administered belumosudil 200 mg QD (n = 20), belumosudil 200 mg BID (n = 20), or matched placebo (n = 20) for 28 weeks. The study will be double-blinded for the first 28 weeks followed by an open-label extension of 24 weeks. After unblinding, the subjects in Group 1 and 2 will continue on the same belumosudil dose whereas the subjects in the placebo group will be re-randomized to one of the belumosudil doses (200 mg QD or 200 BID) in 1:1 fashion.

Efficacy will be assessed throughout the 52-week dosing period using CRISS, mRSS, PFTs, physician global assessment, SHAQ-DI.

[figure not shown]

Figure 1 KD025-209 Study Schema

be on a stable dose for at least 6 months prior to screening

2.3 Visit Schedule and Study Assessment

The flow chart of visit schedule and study assessments is given in Appendix A of the KD025-209 Protocol.

2.4 Treatment Descriptions

The treatment groups will be described below and used for different analysis.

KQD: KD025 200mg QD for the first 28 weeks

KBID: KD025 200mg BID for the first 28 weeks

PBO: Placebo for the first 28 weeks

KQD/KQD: KD025 200mg QD for the first 28 weeks and KD025 200mg QD from week 28 to 52.

KBID/KBID: KD025 200mg BID for the first 28 weeks and KD025 200mg BID from week 28 to 52.

K: KD025 200mg for the first 28 weeks

PBO/KQD: Placebo for the first 28 weeks and KD025 200mg QD from week 28 to 52.

PBO/KBID: Placebo for the first 28 weeks and KD025 200mg BID from week 28 to 52.

KQD_C: KD025 200mg QD for the first 28 weeks combined with subjects that switched from placebo to KD025 200mg QD from week 28 to 52.

KBID_C: KD025 200mg BID for the first 28 weeks combined with subjects that switched from placebo to KD025 200mg BID from week 28 to 52.

K_C: KD025 200mg for the first 28 weeks combined with subjects that switched from placebo to KD025 200mg from week 28 to 52.

All KD025 200mg QD: KD025 200mg QD for the first 52 weeks combined with subjects that switched from placebo to KD025 200mg QD from week 28 to 52.

All KD025 200mg BID: KD025 200mg BID for the first 52 weeks combined with subjects that switched from placebo to KD025 200mg BID from week 28 to 52.

All KD025: KD025 200mg for the first 52 weeks combined with subjects that switched from placebo to KD025 200mg from week 28 to 52.

3 STATISTICAL METHODS

3.1 General Methods

3.1.1 Analysis Periods

The analysis will be split into three separate periods.

- The Double-Blinded Period analysis will be the period from week 0 to week 24.
- The Double-Blinded Period (0 week 28) will be the period from week 0 to week 28.
- The Combined Double-Blinded Period and Open-Label Period will be the period from week 0 to week 52.

3.1.2 Computing Environment

All statistical analyses will be performed using SAS® Version 9.4 or higher for Windows.

3.1.3 Sample Size Justification

This is an exploratory study; sample size and power are not driven by hypothesis testing. A total of 60 subjects will be randomized (1:1:1) to receive orally administered belumosudil 200 mg QD (n = 20), belumosudil 200 mg BID (n = 20), or matched placebo (n = 20).

3.1.4 General Considerations

General considerations for descriptive statistics, presentation, and analysis model (for efficacy analysis) used for continuous and categorical data are given below.

3.1.4.1 Continuous variables

Continuous variables will be described by using these descriptive statistics: number of observations (n), mean, standard deviation (SD), median, minimum and maximum.

The means, medians, SD, and confidence intervals (CIs) will be reported to one decimal place more than the data reported on the case report form (CRF) or by the laboratory/vendor. Minimum and maximum will be reported to the same number of decimal places displayed on the CRF or by the laboratory/vendor. P-values will be reported to 4 decimal places.

3.1.4.2 Categorical Variables

Frequencies and percentages will be used to describe categorical variables. Some efficacy endpoints with two possible outcomes such as CRISS60 response will be analyzed using logistic model, which is defined in Section 3.1.4.3. When categorical data are presented, the percent will be suppressed when the count is zero in order to draw attention to the nonzero counts. The denominator for all percentages, unless otherwise specified, will be the number of subjects in the treatment group or in the specified analysis population.

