Subject status was collected at screening, Week 1 Day 1 (baseline), and for the evaluation of primary and secondary study endpoints. Response was assessed by PASI, PGA, and DLQI scores at scheduled time points throughout the study.

Subjects underwent medical history evaluations; physical examinations ([PEs] including weight, skeletal, and neurological measurements); vital sign measurements; adverse event (AE) assessments; concomitant medication assessments; blood sample collection for hematology, chemistry, coagulation, lipid panel, and thyroid-stimulating hormone; urinalysis; pregnancy testing for females of childbearing potential; photography (optional); punch biopsy (optional); and electrocardiogram (ECGs).

If a subject discontinued from the study prior to 16 weeks, an Early Termination Visit was performed, and procedures were conducted immediately upon discontinuation. For all subjects, including those who discontinued from the study prematurely, a Follow-Up visit occurred 30 days (± 3 days) after the last dose of study drug.

A placebo control was used in the Double-blind Period of this study. No control was used for the Open-label Continuation Period of the study.

A total of 110 subjects were randomized and included in the mITT Population: 23 subjects in the belumosudil 200 mg QD cohort, 22 in the belumosudil 200 mg BID cohort, 21 in the belumosudil 400 mg QD cohort, 26 in the belumosudil 600 mg/day cohort, and 18 in the placebo

cohort. The Safety Population had the same number of subjects as the mITT Population. Of the 110 subjects in the study, 27.3% (n = 30 subjects) completed treatment: 39.1% (n = 9) in the belumosudil 200 mg QD cohort; 27.3% (n = 6) in the 200 mg BID cohort; 42.9% (n = 9) in the 400 mg QD cohort; 15.4% (n = 4) in the 600 mg/day cohort; and 11.1% (n = 2) in the placebo cohort. Overall, the most frequent reasons for early study termination were withdrawal by subject (40.9%; n = 45 subjects), followed by loss to follow-up (12.7%; n = 14 subjects), and elevated liver enzymes (5.5%; n = 6 subjects).

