3.2 Analysis Populations

Three populations will be employed in the analysis of study data:

- The Modified Intent-to-treat (mITT) Population will consist of all subjects who receive at least 1 dose of study drug.
- The Evaluable for Efficacy/Activity Population will consist of subjects who have received at least 80% of expected study drug and have post-baseline efficacy data.
- The Safety Population is defined as all subjects who receive at least 1 dose of study drug. In this study, the Safety Population is equivalent to the mITT Population.

The primary endpoint will be analyzed on the modified Intent-to-Treat (mITT) Population.

Demographics, subject disposition, baseline characteristics, and efficacy analyses will be summarized in mITT Population and by group.

All safety analyses will be performed on the safety population.

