3.8.2.6 HRCT

Changes in lung fibrosis for patients with ILD at screening will be assessed using HRCT. Pure Ground-Class Opacity, Pulmonary Fibrosis and Honeycombing were recorded for each lung and three lung zones. They are recorded categorically for the amount detected, ranging from Absent to >75%. These will be summarized and change from baseline will be compared between treatment groups.

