3.9 Safety Analysis

Safety assessments include AEs, serious adverse events (SAEs), vital sign measurements, clinical laboratory evaluations (hematology, chemistry) and electrocardiograms (ECGs). Unscheduled visits for safety assessments will not be presented in by visit summary tables but will be in listings and shift tables. All safety analyses will be performed using the safety population.

Clinically significant PE findings will be captured as AEs.

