3.9.4 ECG

Descriptive statistics for ECG parameters (i.e., heart rate, PR interval, RR interval, QRS interval, QT interval, and QTcF interval) at each time point with triplicate ECGs will be presented for the values and change from baseline scores (QTcF is the QT interval using Fridericia's correction which is calculated by QTcF = QT/RR^{1/3}). In addition the maximum change from baseline will be calculated for each subject and summarized for each treatment group.

The number and percentage of subjects with observed QTcF values that satisfy the following conditions will be presented by treatment group and study visit:

- ≤ 450 millisecond (ms)
- $>450 \text{ to} \le 480 \text{ ms}$
- >480 to ≤ 500 ms
- > 500 ms

The number and percentage of subjects having change from baseline QTcF values that satisfy the following conditions will be presented by treatment group and study visit:

- ≤ 0 ms
- >0 to ≤ 30 ms
- >30 to ≤ 60 ms
- > 60 ms

A by patient by visit listing will be generated for ECG results.

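### By-visit QTcF category percentages are divided by everyone in the group, and a value above 500 ms seen only on an unscheduled ECG enters no QTcF category table

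*SAP*

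**What the plan says.** **Denominator.** SAP 3.1.4.2 states: "The denominator for all percentages, unless otherwise specified, will be the number of subjects in the treatment group or in the specified analysis population". Safety analyses use the Safety Population, and SAP 3.2 says "The Safety Population is defined as all subjects who receive at least 1 dose of study drug". That number is fixed once dosing starts and does not fall as subjects leave.

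**QTcF categories.** SAP 3.9.4 says "The number and percentage of subjects with observed QTcF values that satisfy the following conditions will be presented by treatment group and study visit". The top category is above 500 ms. A parallel table covers change from baseline, with a top category above 60 ms. Neither table has a denominator of its own.

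**Unscheduled visits.** SAP 3.9 says "Unscheduled visits for safety assessments will not be presented in by visit summary tables but will be in listings and shift tables".

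**Other ECG output in 3.9.4.** There are descriptive statistics by time point. There is also a per-subject extreme: "In addition the maximum change from baseline will be calculated for each subject and summarized for each treatment group". Finally, "A by patient by visit listing will be generated for ECG results". The section defines no ECG shift table and no table of each subject's worst absolute QTcF.

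**Protocol.** Section 5.6 includes a 12-lead ECG among the procedures that may be done at an unscheduled visit. Section 6.2.1 names the mean and maximum change from baseline in QTcF as a safety endpoint. Section 9.6.2 makes QTc above 500 ms a reason to discontinue a subject.

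**The concern.** Two rules, each ordinary when read alone, combine badly for QTcF.

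First, in a by-visit table a fixed denominator treats a missing ECG as if it fell outside the outlier categories. Every category shrinks, including the normal one, so a column adds to less than 100% unless a missing row is shown. The missingness is also not independent of safety: Protocol 9.6.2 removes subjects for QTc above 500 ms and for other toxicities. They then leave the later numerators but stay in the denominators.

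Second, repeat or symptom-driven ECGs may well be recorded as unscheduled. SAP 3.9 sends unscheduled results to listings and shift tables, but the only shift tables the SAP defines are for laboratory grades (3.9.2). For QTcF the shift-table route does not exist.

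At stake is whether the summary tables show how many subjects crossed the threshold that the protocol itself uses for discontinuation.

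**Working it through.** **Inputs from the documents.** Group size N = 20 (SAP 3.1.3); the default denominator (SAP 3.1.4.2); by-visit presentation (SAP 3.9.4); exclusion of unscheduled visits (SAP 3.9).

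**Assumed.** The number m with a QTcF at a visit. The documents give no dropout rate for this trial, so m is varied from 18 to 8 (10% to 60% missing).

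**Plan's own figure.** The plan gives none for these tables. Its one figure tied to 20 per group is the adverse-event detection statement (Protocol 9.9). Using 1 − (1 − p)^20, this gives 95.1% at p = 0.14 and 87.8% at p = 0.10, consistent with the stated lower bounds of 90% and 80%. It is not in dispute.

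**Step 1: size of the denominator effect.** With x subjects in a category:

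printed rate = x/N = (x/m) × (m/N)

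The relative understatement is therefore 1 − m/N, the missing fraction. For x = 2 and N = 20:

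| Measured (m) | Missing | Rate among measured | Printed (2/20) |
|---|---|---|---|
| 18 | 10% | 2/18 = 11.1% | 10% |
| 16 | 20% | 2/16 = 12.5% | 10% |
| 14 | 30% | 2/14 = 14.3% | 10% |
| 12 | 40% | 2/12 = 16.7% | 10% |
| 8 | 60% | 2/8 = 25.0% | 10% |

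With 12 of 20 measured, the four QTcF categories together add to 12/20 = 60%.

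**Step 2: comparison between arms.** Two cases show that the direction is not fixed.

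- Observed rates differ: 2/16 = 12.5% in one arm and 2/8 = 25% in the other. Both print as 2/20 = 10%, and the difference disappears.
- Observed rates are equal: 4/16 = 25% and 2/8 = 25%. They print as 4/20 = 20% and 2/20 = 10%, and a difference appears.

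**Step 3: unscheduled ECGs.** Take one subject whose only QTcF above 500 ms is on an unscheduled ECG.

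- By-visit category tables: SAP 3.9 excludes the value, so it adds 0.
- ECG shift table: none is defined.
- Worst-value category table: none is defined.
- Maximum-change summary: it describes change, so it cannot count absolute values above 500 ms. The SAP does not say whether unscheduled ECGs enter it.

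The above-500 ms row therefore shows 0 at every visit, and SAP 3.1.4.2 suppresses the percentage for a zero count. A worst post-baseline table that included unscheduled ECGs would show 1/20 = 5%.

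**The case against.** The case for leaving the plan alone has real weight.

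- **The value has other routes.** QTc above 500 ms leads to discontinuation (Protocol 9.6.2), and SAP 3.3 summarises the primary reason. An ECG abnormality that changes management is recorded as an adverse event (Protocol 6.2.3), and SAP 3.9.1 repeats the adverse-event tables for events leading to drug discontinuation. The maximum-change summary is not a by-visit table, so the SAP 3.9 exclusion does not clearly apply to it. A reader might infer that such a value would be seen only in a listing. The documents do not support that.
- **The rate can usually be recovered.** SAP 3.9.4 prints counts as well as percentages, and the descriptive statistics by time point include n and the maximum (SAP 3.1.4.1). This stands for scheduled ECGs, at the price of combining two tables. It does not help with unscheduled ones.
- **The named endpoint is covered.** Protocol 6.2.1 asks for mean and maximum change, so the category tables are supplementary. This limits the importance of the point.
- **Measured subjects are a selected group.** When discontinuation depends on the outcome, the rate among those still measured has its own bias and should not be called the true rate. This stands. It is a reason to add a worst post-baseline table, which is less exposed to later dropout, as well as changing the by-visit denominator.
- **ECGs are frequent.** They are scheduled at every visit, and early discontinuers have the end-of-treatment assessments (Protocol 5.4). That reduces the loss, although the SAP has no rule saying under which visit an early end-of-treatment ECG is tabulated.

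A reader might also extrapolate from the psoriasis study in Protocol 1.4.1.3, where "27.3% (n = 30 subjects) completed treatment", and conclude that QTcF signals would be hidden. That study concerned another disease, and its placebo arm completed least: 2/18 = 11.1%, against 9/23 = 39.1% on 200 mg QD and 6/22 = 27.3% on 200 mg BID. With equal observed rates, a fixed denominator would shrink placebo most and suggest a drug effect. It supports neither a size nor a direction here.

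Nor does the default clearly misstate the HRCT categories. SAP 3.8.2.6 says "Changes in lung fibrosis for patients with ILD at screening will be assessed using HRCT", which is naturally read as naming the population to divide by.

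**Conclusion.** The point holds as a defect in two stated reporting rules. As written, by-visit QTcF category percentages are understated, relative to subjects measured, by exactly the fraction not measured at that visit. For 2 outliers in a group of 20, that is 10% printed against 11.1% to 25.0% over an assumed 10% to 60% missing. If every subject is measured at every visit, the effect is nil. The effect on the comparison between arms depends on which arm has more missing ECGs, and the documents do not allow a prediction; a general bias towards showing no QTcF signal cannot be concluded.

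A QTcF above 500 ms that occurs only on an unscheduled ECG enters none of the planned QTcF category tables: 0 shown, where a per-subject worst-value table would show 1 of 20 (5%). That conclusion needs no dropout assumption. It concerns those tables only and does not mean that the event goes unreported.

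The study is exploratory and its safety tables are descriptive, so no inference fails. The correction is still worth making, because the threshold concerned is one the protocol acts on and the data are already collected.

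**What to change.** 1. In SAP 3.1.4.2 or 3.9.4, state that by-visit QTcF percentages use subjects with a non-missing QTcF at that visit and, for change categories, also a non-missing baseline. Print that number in each column.
2. In SAP 3.9.4, add one per-subject table of worst post-baseline QTcF by treatment period, using the existing absolute-value and change categories. Include unscheduled ECGs, and use as denominator the subjects with at least one post-baseline ECG in that period. For placebo subjects who switch, take the open-label baseline already defined in SAP 3.1.6.
3. State that the maximum-change summary includes unscheduled ECGs.

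The cost is two sentences of SAP wording and one extra table. No new data are needed and trial conduct does not change. The changes should be made before database lock.
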